4.1.1.2.2. Treatment Period

Randomization (Visit 3)

At Visit 3, eligible participants (who meet all applicable inclusion criteria and none of the applicable exclusion criteria) will perform all required randomization study procedures (including the collection of all baseline laboratory measures, electrocardiograms (ECGs), and questionnaires) prior to randomization and prior to taking the first dose of study drug.

Participants should arrive at the clinic in the fasting state (after a period of approximately 8 hours without eating, drinking [except water], or any significant physical activity and before taking AHMs). Patient-reported outcomes questionnaires should be administered as early as possible in the visit, as per Suggested Visit Structure (Section 10.8). Preferred administration order:

1. PGIs
2. SF-36v2 acute form
3. IWQOL-Lite-CT
4. EQ-5D-5L

The mental health questionnaires (Patient Health Questionnaire-9 [PHQ-9], Columbia-Suicide Severity Rating Scale [C-SSRS], and Self-Harm Form) should be completed after the assessment for AEs.

Participants will receive an initial consultation with a dietician, or equivalent qualified delegate, according to local standards. Lifestyle goals for caloric intake and physical activity will be set (Section 5.3).

Following randomization, study site personnel will demonstrate use of the autoinjector (also referred to as single-dose pen) using the provided demonstration device and observe the study participant inject the first dose of tirzepatide or placebo. The date, time, and location of the first dose of study drug will be recorded on the electronic case report form (eCRF). Beginning at randomization, all participants will receive study drug according to the randomized treatment arm for the duration of the 72-week treatment period including a dose escalation period of up to 20 weeks.

Treatment Period (End of Visit 3 to Visit 21)

During the treatment period, office visits will occur monthly through 24 weeks and then every 12 weeks thereafter, to 72 weeks. The participant should be fasting for all office visits.

Telephone visits will occur at 4-week intervals between the office visits starting at Week 28.

Office visit procedures should be conducted according to the SoA (Section 1.3), and will include:

- weight, waist circumference, and vital signs measurements
- laboratory testing
- administration of PROs questionnaires
- collection of AEs, product complaints (PCs), and concomitant medications
- review of SMBG values and hypoglycemic events collected in the diary
- Mental Health questionnaires
- review of participant diary information (to include reinforcement and compliance assessments for study drug administration and lifestyle goals)
- study drug and supplies dispensing

Patient-reported outcomes questionnaires should be administered as early as possible in the visit, as per Suggested Visit Structure (Section 10.8). Preferred administration order is the same as Randomization visit.

Mental Health questionnaires should be completed after the assessment of AEs.

Lifestyle consultations continue at Weeks 4, 8, 12, and then every 12 weeks thereafter, to Week 72. Study drug and injection supplies will be returned per the SoA (Section 1.3) and according to local requirements. New supplies will be dispensed as needed.

Study drug dose escalation is double-blinded and will be managed via the interactive web-response system (IWRS). The starting dose is 2.5 mg QW (or matching placebo) for 4 weeks, then the dose is increased by 2.5 mg (or matching placebo) every 4 weeks (2.5 to 5 to 7.5 to 10 mg) for those randomized to 10 mg, continuing to 12.5 to 15 mg for those randomized to 15 mg. The dose is then maintained for the remainder of the study. In participants who experience intolerable GI symptoms, the dose can be changed as described in the Section 6.6.2.

At each of the 8 scheduled telephone visits, procedures will include:

- collection of AEs, PCs, and concomitant medications
- review of SMBG values and hypoglycemic events collected in the diary

- administration of Mental Health questionnaires
- review of participant diary information (to include reinforcement and compliance assessments for study drug administration and lifestyle goals)

Participants should be instructed to contact the investigative site for assistance as soon as possible if they experience any difficulties administering their study medication. Participants should also be advised about the appropriate course of action in the event that study drug is not taken at the required time (late/missing doses).

Study participants will be permitted to use concomitant medications that they require during the study, except certain excluded medications (see Section 5.2) that may interfere with the assessment of efficacy and safety characteristics of the study treatments.

Visit 99

Visit 99 is only applicable to participants who discontinue the study treatment prematurely (before Week 72) and decline to complete the remaining scheduled study visits. These participants will be asked to return for Visit 99 at 72 weeks \pm 7 days after randomization (See Section 7.2.1.). This visit is critical to ensure complete data collection for the primary weight loss endpoint.

Participants should attend this visit in the fasting state. Procedures to be completed are:

- measurement of weight and waist circumference
- listing of concomitant medications
- assessment of AEs, and
- completion of the Mental Health questionnaires (after the AE assessment).

For participants unwilling to attend this visit, their refusal to attend should be documented in the participant medical record.

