1.3. Schedule of Activities (SoA)

The Schedule of Activities described below should be followed for all participants enrolled in Study GPHL. However, for those participants whose participation in this study is affected by exceptional circumstances (such as pandemics or natural disasters), please refer to Section 10.11 Appendix 11 for additional guidance.

Visit	1	2	3	4	5	6	7	8	9	10	11	12	13	14	15	16	17	18	19	20	21	99	ED	801
Week of Treatment	-3	-2	0	4	8	12	16	20	24	28	32	36	40	44	48	52	56	60	64	68	72	72		4 wks post end of TxP
Allowable Interval Tolerance (days)		±3	±7	±3	+7	±3	+7	±3	±3	±3	±3	+7	±3	±3	±3	±3	±3	±3	±3	±3	±7	±7		±3
Fasting Visit	X		X	X	X	X	X	X	X			X			X			X			X	X	X	X
Telephone Visit										X	X		X	X		X	X		X	X				
Informed consent	X																							
Inclusion and exclusion criteria review	X	X	X																					
Preexisting conditions and medical history, including relevant surgical history	X																							
	Medical history includes assessment of preexisting conditions (for example, history of gallbladder disease, cardiovascular disease, and medullary thyroid carcinoma) and substance usage (such as alcohol and tobacco).																							
Concomitant medications	X	X	X	X	X	X	X	X	X	X	X	X	X	X	X	X	X	X	X	X	X	X	X	X
Adverse events and product complaints	X	X	X	X	X	X	X	X	X	X	X	X	X	X	X	X	X	X	X	X	X	X	X	X
Physical Evaluation or Clinical Assessments																								
Height	X																							
Weight	X		X	X	X	X	X	X	X			X			X			X			X	X	X	X
	Weight measurements should be obtained per the detailed protocol guidance in Section 10.7. Body weight must be measured in the fasting state. If the participant is not fasting, the participant should be called in for a new visit within the visit window to have the fasting body weight measured.																							
Waist circumference			X	X	X	X	X	X	X			X			X			X			X	X	X	X
Vital signs (systolic and diastolic blood pressure, pulse rate)	X		X	X	X	X	X	X	X			X			X			X			X		X	X
	Vital sign measurements should be taken before obtaining an ECG tracing and before collection of blood samples for laboratory testing, per the instruction in Section 10.7.																							

Visit	1	2	3	4	5	6	7	8	9	10	11	12	13	14	15	16	17	18	19	20	21	99	ED	801
Week of Treatment	-3	-2	0	4	8	12	16	20	24	28	32	36	40	44	48	52	56	60	64	68	72	72		4 wks post end of TxP
Allowable Interval Tolerance (days)		±3	±7	±3	+7	±3	+7	±3	±3	±3	±3	+7	±3	±3	±3	±3	±3	±3	±3	±3	±7	±7		±3

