Observe participant administer study drug			X																						
Participants should administer their first dose of study drug at the end of the Visit 3, after other study procedures and randomization have been completed.																									
Participant returns study interventions and injection supplies				X	X	X	X	X	X			X			X			X			X		X		
Assess study intervention(s) compliance				X	X	X	X	X	X	X	X	X	X	X	X	X	X	X	X	X	X	X		X	

Abbreviations: BG = blood glucose; CKD-EPI = Chronic Kidney Disease-Epidemiology; ECG = electrocardiogram; eCRF= electronic case report form; ED = early treatment discontinuation; eGFR = estimated glomerular filtration rate; HbA1c = hemoglobin A1c; HR=heart rate; IWQOL-Lite-CT = Impact of Weight on Quality of Life-Lite-Clinical Trials Version; IWRS = interactive web-response system; PGIs = Patient Global Impression of status for physical activity; PK = pharmacokinetics; SF-36v2 acute form = Short Form-36 Version 2 Health Survey acute form; SMBG = self-monitoring of blood glucose; SoA = Schedule of Activities; TxP = treatment period; TZP= tirzepatide; wks = weeks.

Note:

- Visit 3 baseline assessments must be completed before processing the randomization in the IWRS.
- The visit date is determined in relation to the date of Visit 3 (randomization).

- Visit 99 is only applicable to participants who discontinue the double-blind study treatment prematurely and decline to complete the remaining scheduled study visits. Participants wanting to discontinue the study before Week 72 will be asked to return for Visit 99, 72 weeks \pm 7 days after randomization, primarily for body weight measurement and assessment of adverse events. If the participant is unwilling to attend Visit 99, it should be documented in the participant medical record that the participant has refused to attend.
- Participants who are unable or unwilling to continue the study treatment for any reason will perform an ED visit. If the participant is discontinuing during an unscheduled visit or a scheduled visit, that visit should be performed as an ED visit.
- Visit 801 (safety follow-up visit) should be performed 4 weeks after the last visit of the participant's treatment period (see Section 7.2.1.).

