4.1.1.3. Safety Follow-up Period

Visit 801

All participants are required to complete a safety follow-up visit (Visit 801), according to the SoA. Participants discontinuing the study early and performing an ED visit will also be asked to perform the safety follow-up visit. During the safety follow-up period, participants will not receive study drug. Participants may be treated with another glucose-lowering intervention at the discretion of the investigator or participant's usual diabetes care physician (see Section 6.5.2). If any new AHM is initiated during the safety follow-up period, it will not be classified as rescue

therapy (see Section 6.5.3.1). Participants are also required to return any remaining study diaries to the study site at the end of this period.

For participants who discontinue or complete the study, Visit 801 (safety follow-up visit) should be performed 4 weeks after the last visit of the treatment period (Visit 21 or 99) or 4 weeks after the ED visit for those who decline to return for Visit 99.

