6.6.2. Management of Participants with Gastrointestinal Symptoms

Participants who experience intolerable GI symptoms (for example, nausea, vomiting, or diarrhea) at any time during the study should first be counseled on dietary behaviors that may help mitigate nausea and vomiting (for example, eating smaller meals, splitting 3 daily meals into 4 or more smaller ones, and stopping eating when they feel full) (see Section 10.9). If symptoms persist, the participant should be prescribed, at the investigator's discretion, symptomatic medication (for example, antiemetic or antidiarrheal medication). A temporary interruption of study drug for 1 dose is permitted, provided the participant has taken the last 3 weekly doses. Study treatment should be resumed immediately, either alone or in combination with symptomatic medication, which can also be utilized to manage symptoms. Management of study drug after interruptions >1 dose is discussed in Section 7.1.1.

If intolerable GI symptoms (for example, nausea, vomiting, or diarrhea) persist despite the above measures, the investigator should contact Lilly to consider reinitiating study drug at the next-lower maintenance dose in a blinded fashion (for example, 15 mg and 12.5 mg reduced to 10 mg, 10 mg or lower reduced to placebo). Only 1 dose reduction per participant will be permitted during the course of the study.

If intolerable GI symptoms persist despite symptomatic treatment, temporary drug interruption, and resumption at a lower dose of study drug, the participant should be discontinued from the study drug. All participants who discontinue study drug should continue to attend scheduled study visits. All dose adjustments will be managed through IWRS.

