- in addition, study drug may be discontinued if participants:
 - answered "yes" to Question 4 (Active Suicidal Ideation with Some Intent to Act, Without Specific Plan) on the "Suicidal Ideation" portion of the C-SSRS
 - or**
 - answered "yes" to Question 5 (Active Suicidal Ideation with Specific Plan and Intent) on the "Suicidal Ideation" portion of the C-SSRS
 - or**
 - answered "yes" to any of the suicide-related behaviors (Actual attempt, Interrupted attempt, Aborted attempt, Preparatory act or behavior) on the "Suicidal Behavior" portion of the C-SSRS

Note: A psychiatrist or appropriately trained professional may assist in the decision to discontinue the participant.

- **Discontinuation due to a hepatic event or liver test abnormality**

- Participants who are discontinued from IP due to a hepatic event or liver test abnormality should have additional hepatic safety data collected via eCRF
- Discontinuation of the IP for abnormal liver tests **should be** considered by the investigator when a participant meets 1 of the following conditions after consultation with the Lilly designated medical monitor:
 - ALT or aspartate aminotransferase (AST) $>8X$ ULN
 - ALT $>2X$ baseline value or ≥ 300 U/L, whichever occurs first, if baseline ALT $\geq 2X$ ULN
 - ALT or AST $>5X$ ULN for more than 2 weeks
 - ALT or AST $>3X$ ULN and TBL $>2X$ ULN or international normalized ratio (INR) >1.5

- ALT or AST >3X ULN with the appearance of fatigue, nausea, vomiting, right-upper-quadrant pain or tenderness, fever, rash, and/or eosinophilia (>5%)
- ALP >3X ULN
- ALP >2.5X ULN and TBL >2X ULN
- ALP >2.5X ULN with the appearance of fatigue, nausea, vomiting, right-upper-quadrant pain or tenderness, fever, rash, and/or eosinophilia (>5%)

Participants who stop the study drug permanently should continue to attend all scheduled study visits to collect all planned efficacy and safety measurements. Participants who stop the study treatment post-randomization and prior to 72 weeks but are unwilling to attend remaining scheduled visits should return for Visit 99 for a final weight measurement. If these participants are unwilling to attend Visit 99, their refusal to attend should be documented in the patient medical record.

See the SoA for data to be collected at the time of intervention discontinuation and follow-up and for any further evaluations that need to be completed.

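### Visit 99 takes no blood pressure or blood sample, so participants seen only there have no Week-72 SBP, HbA1c, glucose or lipid value; a standard blood pressure set would close the gap for SBP

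*Protocol*

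**What the plan says.** **Visit 99.** Protocol 4.1.1.2.2 asks participants who stop drug early and decline their remaining visits to return, fasting, 72 weeks after randomization. The only physical measurements listed are "measurement of weight and waist circumference". The other items are concomitant medications, adverse events and mental health questionnaires. The purpose is stated: "This visit is critical to ensure complete data collection for the primary weight loss endpoint". The notes to the Schedule of Activities (SoA) describe the visit as "primarily for body weight measurement and assessment of adverse events".

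SAP 1.2 gives the same items, though its lead-in does not present them as exhaustive. It also applies the visit to anyone who stops treatment early and leaves out the condition about declining further visits.

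**SoA.** The vital signs and HbA1c rows are marked at Visit 21, the early discontinuation (ED) visit and Visit 801, and are blank at Visit 99. The chemistry and lipid rows are partly misaligned in the text available to me, so for glucose and lipids I rely on the list in Protocol 4.1.1.2.2.

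**Other visits.** The default after stopping drug is full attendance: "Participants who stop the study drug permanently should continue to attend all scheduled study visits to collect all planned efficacy and safety measurements" (Protocol 7.1). After Visit 99 comes safety follow-up: "All participants are required to complete a safety follow-up visit (Visit 801), according to the SoA" (Protocol 4.1.1.3), timed four weeks after Visit 99.

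**Analysis.** SAP 2 and 4.4.1 make SBP, HbA1c, fasting glucose, triglycerides, HDL and non-HDL cholesterol type-I-controlled endpoints at Week 72. For the FDA they follow the treatment-regimen estimand. SAP 4.1 and 4.4.1 send missing Week-72 values to the hybrid imputation of SAP 4.3.2.3. That method draws on same-arm participants assessed after stopping drug (retrieved dropouts) and falls back on the placebo arm if there are too few. SAP 3 limits the Full Analysis Set (FAS) to treatment-period data.

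**The concern.** The treatment-regimen estimand deliberately keeps people who have stopped drug. Those who come only to Visit 99 are on site and fasting at Week 72, and they count as retrieved dropouts for weight and waist. For SBP, HbA1c, glucose and lipids they are missing and must be imputed.

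Donors for those endpoints are then only the drug-stoppers who agreed to full visits. That pool is smaller and may not represent the others. A smaller pool also makes the placebo fallback somewhat more likely. At stake are the precision and representativeness of off-drug values on type-I-controlled secondary endpoints.

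**Working it through.** **1. The plan's own figure.** Protocol 9.2 and SAP 5 state more than 90% power for the weight co-primaries. With 300 × (1 − 0.25) = 225 evaluable per arm, a difference of 11, SD 10 and two-sided alpha 0.025, the standardized signal is 11 / (10 × √(2/225)) = 11.7, so power is about 100%. For 25% against 90% responders, power is also about 100%. The statement holds, and Visit 99 supports it. No effect, SD or power is given for SBP, HbA1c, glucose or lipids.

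**2. Endpoints not measured at Visit 99.** SAP 2 has nine by-dose key secondary endpoints on two doses and four pooled ones: 9 × 2 + 4 = 22 hypotheses.

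| Measurement | Key secondary hypotheses | Taken at Visit 99 |
|---|---|---|
| Weight thresholds (≥10%, ≥15%, ≥20%) | 6 | yes |
| Waist | 2 | yes |
| HbA1c (change and three targets) | 8 | no |
| Fasting glucose | 2 | no |
| Triglycerides, HDL, non-HDL | 3 | no |
| SBP (Hp,11) | 1 | no |

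Fourteen hypotheses rest on measurements not taken at Visit 99. One of them is SBP.

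**3. Whether another visit supplies the value.** The ED visit and Visit 801 both include vital signs and HbA1c. The ED value is taken when treatment stops, not at Week 72. The Visit 801 value comes at about Week 76, in the safety follow-up period, and so lies outside the FAS. Neither is a Week-72 observation. I read SAP 4.3.2.3, which is worded for the primary outcome, as applying to each key secondary in turn, since SAP 4.1 and 4.4.1 send those endpoints to it.

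**4. Illustrative size.** The documents do not give the number who attend only Visit 99. Assumptions:
- share off drug w = 15% or 25% (25% is the planning dropout rate, borrowed only as a scale);
- share of those attending only Visit 99 = 20% or 40%;
- a further 20% of those off drug not seen at Week 72;
- equal SD on and off drug, and equal shares in all arms.

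Affected per arm: from 300 × 0.15 × 0.20 = 9 to 300 × 0.25 × 0.40 = 30 (3–10%).

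For an arm of 300, with r the correlation of the ED value with Week 72, n_off = 300w and d donors:

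Var(arm mean)/SD² = (1 − w)/300 + w² × [(1 − r²)/d + r²/n_off]

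Example with w = 0.25 and r = 0.7:
- 60 donors (Visit 99 measured): 0.00250 + 0.0625 × (0.51/60 + 0.49/75) = 0.00344
- 30 donors (40% attend only Visit 99): 0.00250 + 0.0625 × (0.51/30 + 0.49/75) = 0.00397
- ratio of standard errors: √(0.00397/0.00344) = 1.074

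| w | Donors if Visit 99 measured | Donors as planned | SE ratio, r = 0.7 | SE ratio, r = 0 |
|---|---|---|---|---|
| 0.15 | 36 | 27 | 1.016 | 1.030 |
| 0.15 | 36 | 18 | 1.046 | 1.087 |
| 0.25 | 60 | 45 | 1.025 | 1.048 |
| 0.25 | 60 | 30 | 1.074 | 1.138 |

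With equal shares across arms, the same ratio applies to the contrast with placebo, including pooled doses against placebo.

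**The case against.** The strongest defence is that Visit 99 is short on purpose. It serves people who have already refused further visits, and each added procedure risks attendance for the primary endpoint. The default is the full schedule, as Protocol 6.6.2 repeats for gastrointestinal intolerance: "All participants who discontinue study drug should continue to attend scheduled study visits". Missing key secondary values have a prespecified method. Every input to the size is assumed, and Protocol 7.1 describes permanent discontinuation as rare.

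Much of this stands. It is a good reason not to require blood sampling, and the size can only be illustrated. The 14% end needs an imputation model with no predictor, which the SAP does not specify. The defence is weak for blood pressure. Participants are already being weighed and having their waist measured, and Protocol 4.1.1.3 asks them back four weeks later for a visit that includes vital signs.

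A reader might infer three stronger claims that the documents do not support:
- **That efficacy is inflated.** The direction of any bias is unknown. Donors willing to attend full visits could differ from the others either way, and the placebo fallback would generally pull tirzepatide toward placebo.
- **That key secondary power is inadequate.** No planning effect, SD or power is stated for these endpoints, so a larger standard error cannot be turned into a power loss for any of these hypotheses.
- **That adding blood pressure repairs all fourteen hypotheses.** It repairs one.

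**Conclusion.** The gap is real and limited. Participants seen only at Visit 99 have no Week-72 SBP, HbA1c, fasting glucose or lipid value for the treatment-regimen analysis, and they cannot be retrieved-dropout donors for those endpoints. The co-primaries, weight responders and waist are unaffected. So are drug-stoppers who keep the full schedule, and the efficacy estimand, whose analysis set excludes data after drug is stopped.

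Under the stated assumptions the standard error is about 2–7% larger with an ED predictor correlated 0.7, and up to 14% larger with none. This is a cheap improvement, not a flaw that threatens the trial's conclusions. Certainty is highest for SBP and HbA1c, where list and schedule agree. For glucose and lipids it rests on the protocol list. The disposition diagram in Protocol 7.2.1 could not be read.

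**What to change.** 1. Add seated blood pressure to Visit 99 in Protocol 4.1.1.2.2, SAP 1.2 and the SoA Visit 99 column. Use the Appendix 7 method: five minutes of sitting quietly, then two readings at least one minute apart with an automated device. A single reading would not match Visit 21. This closes the gap for Hp,11 among those who attend; people who refuse Visit 99 stay missing.
2. Reconcile Protocol 4.1.1.2.2 and SAP 1.2 on who attends Visit 99.

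Optional HbA1c, chemistry and lipid samples at the same fasting visit could partly close the gap for the other 13 hypotheses. That trades against attendance, so it is for the sponsor to weigh and is not part of the firm fix.

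The cost is a slightly longer Visit 99, a protocol amendment with the usual ethics and authority approvals and any reconsent, and a short SAP edit.
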